2.2.3 Safety Endpoints

Analysis of safety endpoints will be conducted using the SS only.

- AEs

All AEs will be summarized by number and proportion of subjects and number of AEs. TEAEs will be summarized by calculating the number and percent of subjects with AEs by MedDRA primary system organ class (SOC) and preferred term (PT). Also, TEAEs will be summarized by severity and relationship to treatment. Number and percent of subjects with serious TEAEs, TEAEs leading to trial termination and TEAEs of special interest will be provided by MedDRA PT and SOC.

- Vital signs

Summary statistics for absolute values and absolute change from V1a (baseline) will be provided for each visit (V1b to V6/EDV).

- Clinical laboratory parameters

Laboratory parameters will be summarized by calculating summary statistics on the absolute values and on the change from V1a to V3, V4, V5 and V6. Shift tables will be provided to illustrate changes with respect to the laboratory normal ranges between V1a and V6/Early discontinuation visit (EDV). The number and percent of subjects with values outside the limits of clinical significance reference ranges will be summarized.

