3.2 Subgroups

The following subgroups will be defined:

- Weight subgroups, defined as
 - < median weight of the safety set
 - \geq median weight of the safety set
- Body mass index (BMI) subgroups, defined as
 - $BMI < 30 \text{ kg/m}^2$
 - $BMI \geq 30 \text{ kg/m}^2$
 - $25 \text{ kg/m}^2 < BMI < 30 \text{ kg/m}^2$ ¹
- Blood pressure subgroups, defined as
 - Systolic blood pressure (SBP) $< 130 \text{ mmHg}$ and diastolic blood pressure (DBP) $< 85 \text{ mmHg}$
 - Systolic blood pressure (SBP) $\geq 130 \text{ mmHg}$ or diastolic blood pressure (DBP) $\geq 85 \text{ mmHg}$
- Race subgroups, defined as
 - American Indian or Alaska Native
 - Asian
 - Black or African-American

¹ $25 \text{ kg/m}^2 < BMI < 30 \text{ kg/m}^2$ category is in addition to the protocol.

- Native Hawaiian or Other Pacific Islander
- White
- Other
- Ethnicity subgroups, defined as
 - Hispanic or Latino
 - Not Hispanic or Latino

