4.6 Trial Periods

Date of the first IMP intake

The date of the first IMP intake will be defined as the date of the first IMP intake recorded in the treatment diary.

If such date is not available and subject did not return all IMP pills, Visit 1b date will be taken into account.

Date of the last IMP intake

The date of last IMP intake will be defined as the date of the last IMP intake provided in the eCRF “Trial Termination” section.

If such date is incomplete the following will be imputed:

- The date of the last day of the month, if month and year is available but the day is missing.

If such date is not available or only year is provided, last date of IMP administration recorded in subject's diary will be taken into account. If last date of IMP administration recorded in subject's diary is not available and subject did not return all IMP pills, the subject's last visit date will be taken into account.

Treatment period

The treatment period is defined as the period from the first IMP intake up to the last IMP intake.

Baseline value

Baseline value for a variable will be defined as Visit 1a value.

Absolute change

Absolute change from Visit 1a to each visit will be calculated as

$$\text{Absolute change from Baseline at Visit } <X> = \text{Value at Visit } <X> - \text{Baseline Value.}$$

Treatment cycle

Treatment cycles will be defined as 28 days periods starting on the day of the first IMP intake from the blister containing 28 tablets. No more than 13 completed cycles will be used for analysis.

Reference period

The treatment period will be grouped into reference periods as:

- Cycles 2-4
- Cycles 5-7
- Cycles 8-10
- Cycles 11-13

Overall period

- Cycles 2-13

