5.2 Demographic and Other Baseline Characteristics**5.2.1 Demographics**

Demographic data collected at Visit 1a will include the following:

- Date of birth
- Ethnicity (Hispanic or Latino, Not Hispanic or Latino)
- Race (American Indian or Alaska Native, Asian, Black or African American, Native Hawaiian or Other Pacific Islander, White, Other)
- Highest level of education completed (No high school diploma, high school diploma or equivalent, some college, college degree or higher)
- Years of education completed for subjects who have no high school diploma
- Sexual activity.

Age in years

Age in years will be calculated as the difference between the date of birth and the date of informed consent/assent using the following SAS function:

Age = FLOOR(YRDIF(< date of informed consent >, < date of birth >, 'ACT/ACT'))

Breastfeeding

With Protocol Final Version 4.0, 16 November 2015 exclusion criteria have been changed and breastfeeding women were allowed to enter the study. Information on whether the subject is breastfeeding will be collected in the eCRF only on Protocol Final Version 4.0, 16 November 2015.

Additional categories which will be presented in demographic and subgroup tables:

- Breastfeeding status, defined as
 - Breastfeeding
 - Non-breastfeeding

- Age categories (the 1st rule), defined as
 - ≤35 years (at study enrollment)
 - >35 years (at study enrollment)
- Age categories (the 2nd rule), defined as
 - 15-17 years (at study enrollment)
 - 18-35 years (at study enrollment)
 - >35 years (at study enrollment)
- Non-breastfeeding women and race, defined as:
 - Non-breastfeeding women, American Indian or Alaska Native
 - Non-breastfeeding women, Asian
 - Non-breastfeeding women, Black or African-American
 - Non-breastfeeding women, Native Hawaiian or Other Pacific Islander
 - Non-breastfeeding women, White
 - Non-breastfeeding women, Other
- Non-breastfeeding women and BMI, defined as:
 - Non-breastfeeding women, BMI < 30 kg/m²
 - Non-breastfeeding women, BMI ≥ 30 kg/m²
 - Non-breastfeeding women, 25 kg/m² < BMI < 30 kg/m²²
- Sexual activity status, defined as:
 - Active
 - Non-active

Baseline characteristics of the subjects include:

- Body height (cm) at screening visit
- Body weight (kg) at screening visit
- BMI (kg/m²) at screening visit
- Systolic blood pressure (mmHg) at screening visit
- Diastolic blood pressure (mmHg) at screening visit
- Pulse rate (bpm) at screening visit.

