5.6.2 Vital Signs

Vital signs include blood pressure, pulse, height, body weight and BMI data.

Summary statistics for parameter values and absolute parameter change values from Baseline to Visit 6/EDV will be provided for each visit as described in Sections 4.1 and 4.6.

Blood pressure and pulse

Blood pressure and pulse data include:

- Time of first/second/third measurement
- Pulse (bpm)
- Systolic blood pressure (mmHg)
- Diastolic blood pressure (mmHg)

Blood pressure and pulse will be measured in a sitting position at all visits from V1a to V6/EDV, after the subject has rested for at least five minutes.

Median value from the 1st, 2nd and 3rd measurements for systolic, diastolic blood pressure and pulse rate will be summarized in analysis tables. All values from the 1st, 2nd and 3rd measurements for systolic, diastolic blood pressure and pulse rate will be provided in a listing.

Height, body weight and body mass index

Height, body weight and body mass index data include:

- Weight (kg)
- Height (cm)
- Body mass index (kg/m²)

At V1a, height will be measured in all subjects. At V1b to V6 height only has to be determined in adolescent subjects. Body weight will be measured at all visits from V1a to V6/EDV, lightly dressed and without shoes. The determined body weight has to be calculated as BMI. The BMI as a measure for the physical constitution of a ≥18-year-old subject is defined as follows:

$$BMI \text{ at Visit } X \text{ (kg/m}^2\text{)} = \frac{Body \text{ weight at Visit } X \text{ (kg)}}{(Body \text{ height at Visit } 1a \text{ (cm)/100})^2}.$$

The BMI as a measure for the physical constitution of a <18-year-old subject is defined as follows:

$$BMI \text{ at Visit } X \text{ (kg/m}^2\text{)} = \frac{Body \text{ weight at Visit } X \text{ (kg)}}{(Body \text{ height at Visit } X \text{ (cm)/100})^2}.$$

Summary of vital signs will be repeated for defined subgroups.

Tables

No.	Name	Analysis set	Comments
Table 15.3.2.1.1	Summary of Vital Signs	Safety	Vital signs parameters will be summarized descriptively including change from baseline at each visit where assessments were made. Data of centers 104 and 120 will be excluded.
Table 15.3.2.1.2	Summary of Vital Signs by Weight Subgroup	Safety	Vital signs parameters will be summarized descriptively by weight subgroup including change from baseline at each visit where assessments were made. Data of centers 104 and 120 will be excluded.

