Table 15.3.2.1.3	Summary of Vital Signs by BMI Subgroup	Safety	Vital signs parameters will be summarized descriptively by BMI subgroup including change from baseline at each visit where assessments were made. Data of centers 104 and 120 will be excluded.
Table 15.3.2.1.4	Summary of Vital Signs by Blood Pressure Subgroup	Safety	Vital signs parameters will be summarized descriptively by blood pressure subgroup including change from baseline at each visit where assessments were made. Data of centers 104 and 120 will be excluded.
Table 15.3.2.1.5	Summary of Vital Signs by Race Subgroup	Safety	Vital signs parameters will be summarized descriptively by race subgroup including change from baseline at each visit where assessments were made. Data of centers 104 and 120 will be excluded.
Table 15.3.2.1.6	Summary of Vital Signs by Ethnicity Subgroup	Safety	Vital signs parameters will be summarized descriptively by ethnicity subgroup including change from baseline at each visit where assessments were made. Data of centers 104 and 120 will be excluded.

Listings

No.	Name	Analysis set	Comments
Listing 16.2.4.1	Vital Signs (EN)	Enrolled	All vital signs records will be listed.

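### If Visit 1a both defines the blood pressure subgroups (SAP 3.2 names no visit) and is the baseline, the upper group in Table 15.3.2.1.4 is expected to fall with no drug effect

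*SAP*

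**What the plan says.** SAP 4.6 applies one rule to all variables: "Baseline value for a variable will be defined as Visit 1a value". Section 2.2.3 applies it to vital signs, with change from V1a shown at each visit from V1b to V6/EDV.

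Section 3.2, under "Blood pressure subgroups, defined as", gives a lower group (SBP below 130 and DBP below 85 mmHg) and an upper group (SBP at least 130 or DBP at least 85 mmHg). It names no visit. The nearest guidance is Section 5.2.1, which lists among the baseline characteristics "Systolic blood pressure (mmHg) at screening visit".

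For Table 15.3.2.1.4, Section 5.6.2 says: "Vital signs parameters will be summarized descriptively by blood pressure subgroup including change from baseline at each visit where assessments were made". The analysed value at each visit is the median of three readings, which footnote 11 of the visit schedule spaces one minute apart.

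On Visit 1b, Section 5.6.2 says: "Blood pressure and pulse will be measured in a sitting position at all visits from V1a to V6/EDV". The schedule dispenses IMP at V1b, and Section 2.3 places first intake after V1b for naïve and previous users. Section 3.3 also plans Listing DRM12 for first intakes that precede V1b. Section 2.3 describes the trial as non-controlled. Neither document mentions regression to the mean.

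**The concern.** Women placed in the upper group because their value was high at one visit will, on average, read lower at another visit, treated or not. The median of three readings a minute apart reduces noise within the sitting but leaves visit-to-visit variation. When the value that selects the group is also subtracted as baseline, the selected excess goes straight into the change score.

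A randomised comparison would cancel this, but there is no comparator here. A reader of Table 15.3.2.1.4 could take the fall as a blood-pressure-lowering effect, or overlook a true rise of similar size in the women who started with higher values.

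**Working it through.** The documents give no blood pressure mean, SD, between-visit correlation or expected change, so there is no planned figure to reproduce.

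**Inputs from the documents.** The 130/85 rule (SAP 3.2); Visit 1a as baseline (4.6); the entry limits of 159/99 on the screening median (protocol synopsis, inclusion criterion 5); 995 non-breastfeeding women allocated and 45% assumed dropout (protocol synopsis).

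**Assumed inputs.** Mean 110/70 to 120/77 mmHg; SD 10/7 to 12/8.5; SBP-DBP correlation 0.6; between-visit correlation r of the visit-level median 0.5 to 0.8 for SBP and 0.4 to 0.75 for DBP.

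**Model.** Value at visit v = μ + σ(√r·T + √(1−r)·E_v), where T is a stable subject component and E_v an independent visit error. For one variable, expected change in a group selected at V1a = −(1−r) × (group mean at V1a − μ). The either/or rule on two pressures needs simulation: 1,000,000 women per scenario, zero drug effect.

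**Visit 1a in both roles; mean change at a later visit, SBP/DBP in mmHg:**

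| Mean | SD | r | Share in upper group | Upper group | Lower group |
|---|---|---|---|---|---|
| 115/74 | 10/7 | 0.5/0.4 | 10.4% | −7.77/−5.85 | +0.90/+0.68 |
| 115/74 | 10/7 | 0.65/0.55 | 10.4% | −5.49/−4.29 | +0.64/+0.50 |
| 115/74 | 10/7 | 0.8/0.75 | 10.4% | −3.11/−2.41 | +0.38/+0.29 |
| 115/74 | 12/8.5 | 0.5/0.4 | 16.3% | −8.00/−6.17 | +1.58/+1.23 |
| 115/74 | 12/8.5 | 0.65/0.55 | 16.2% | −5.65/−4.54 | +1.11/+0.90 |
| 115/74 | 12/8.5 | 0.8/0.75 | 16.2% | −3.22/−2.54 | +0.63/+0.50 |
| 110/70 | 11/8 | 0.65/0.55 | 5.6% | −7.01/−5.67 | +0.42/+0.36 |
| 120/77 | 11/8 | 0.65/0.55 | 25.9% | −4.32/−3.45 | +1.55/+1.26 |
| 115/74 (central) | 11/8 | 0.65/0.55 | 13.9% | −5.46/−4.57 | +0.90/+0.75 |
| 115/74 | 11/8 | 1/1 | 13.9% | 0/0 | 0/0 |

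**Checks.**
- The fall scales with 1−r, as the formula says: 7.77/3.11 = 2.50 against (1−0.5)/(1−0.8) = 2.5. At r = 1 it vanishes, so the mechanism is regression to the mean.
- The two groups nearly balance. Central case, SBP: 0.139 × (−5.46) + 0.861 × 0.90 = −0.76 + 0.77 ≈ 0.

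**Against sampling noise, central case.** 0.139 × 995 ≈ 138 women; SD of SBP change 8.8; SE = 8.8/√138 ≈ 0.75, so the artefact is about 7 SEs. After 45% dropout, 138 × 0.55 ≈ 76 women; SE = 8.8/√76 ≈ 1.0, so about 5 SEs.

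**Which visit does which job (upper group, later visit):**
- Classify on V1a, baseline V1b: within 0.1 mmHg of zero for SBP and DBP.
- Classify on V1b, baseline V1a: within 0.15 mmHg of zero.
- V1b in both roles: SBP −3.1 to −8.1, DBP −2.4 to −6.3. Nothing is gained.
- Classify on V1a, baseline V1b, with V1a and V1b errors correlated at an assumed 0.3: −1.59/−1.36 remains of −5.41/−4.57, about 30%.

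**The planned V1b row.** With Visit 1a in both roles, the V1a-to-V1b change in the upper group is −5.46/−4.58 in the central case. With independent visit errors, the whole artefact is already visible there.

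**The case against.** The strongest reply is that the plan already displays the artefact. Section 2.2.3 requires change from V1a at V1b, and Table 15.3.2.1.4 covers every visit with an assessment. A careful reader can therefore set the V1b row, normally pre-dose, against the later rows. This largely stands. A reader might infer that nothing in the plan would reveal the fall, and that is not so. What is missing is any statement that V1b is the pre-dose reference; the SAP presents it as an ordinary change-from-baseline row. The comparison across rows is also left to the reader, with membership changing as women drop out.

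Three further objections stand in part.
- The SAP does not say that Visit 1a classifies women. That is inferred from Sections 4.6 and 5.2.1, and the silence of Section 3.2 is itself a gap.
- A reader might infer that the split rests on one cuff reading. It rests on one visit's median of three, which lowers the error but does not remove variation between visits.
- The table is descriptive, with no test attached, and the unstratified Table 15.3.2.1.1 is not split on blood pressure. A reader might infer that the trial's blood pressure findings as a whole, or its primary result, are compromised. The documents do not support that.

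Finally, the sizes rest wholly on assumed parameters. That limits confidence in the magnitude, not in the direction.

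**Conclusion.** The point holds in limited form. Provided Visit 1a both classifies and serves as baseline, the direction needs only a between-visit correlation below 1: the upper group falls and the lower group rises a little with no drug effect. Across the assumed ranges the upper group's fall is 3.1 to 8.0 mmHg SBP and 2.4 to 6.2 mmHg DBP; the lower group's rise is 0.4 to 1.6 and 0.3 to 1.3 mmHg.

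The consequence is possible misreading of one descriptive safety table. The Pearl Index does not depend on it. The change is worth making because it is cheap and the readings are already scheduled. A reader might also infer that moving the general baseline definition to V1b is enough. It is not: if the subgroup follows baseline to V1b, the same fall returns.

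**What to change.** 1. In Section 3.2, name Visit 1a (median of three) as the visit that defines the blood pressure subgroups.
2. For blood pressure in Table 15.3.2.1.4 only, compute change from the Visit 1b median where V1b precedes first IMP intake. For the Listing DRM12 cases, show the values but leave them out of the change.
3. State how a first intake dated on the V1b day is handled, because Section 4.6 can impute the V1b date as the first-intake date.
4. Keep the V1a-to-V1b change in the table, labelled as the pre-dose reference.
5. Leave the general baseline definition in Section 4.6 as it is, and do not give V1b both roles. The schedule shows no routine laboratory sample at V1b, so a general change would not work for laboratory data in any case.

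The cost is SAP wording and one derivation, with no new data. Women without a pre-dose V1b value drop out of this change summary; the documents do not say how many. The subgroup changes will no longer reconcile directly with Table 15.3.2.1.1, which stays on V1a; a footnote covers that. Some artefact remains if V1a and V1b errors are correlated.

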4.7 Visit Windows

No windowing will be done, that is, the data will be analyzed with the nominal visit numbers.

4.8 Complete and correct treatment diary records

Treatment diary records will be defined as correct and complete if the following information will be non-missing:

- Reference date (REFDTC),
- Vaginal bleeding or spotting (VAGBLEEX),
- Bleeding amount (BLEEDAMX).

4.9 Coding Systems and Conventions**4.9.1 Coding of adverse events and medical history**

Adverse event and medical history investigator terms are assigned to a lowest level term (LLT) and a preferred term (PT) and will be classified by high level term (HLT), high level group term (HLGT) and system organ class (SOC) according to the Medical Dictionary for Regulatory Activities (MedDRA), Version 17.0 [2].

4.9.2 Coding of medications

Medications are classified according to active drug substance using the World Health Organization-Drug Dictionary (WHO-DD), version 2014 [3]. The WHO drug code has 11 digits. The generic name is defined by the first 6 of the 11 digits. In addition, the Anatomical Therapeutic Chemical (ATC) classes are assigned to the drug code. In this trial, ATC codes are defined to the 4th level.

4.10 Handling of Missing Data

Handling of missing data, if applicable, is discussed in the relevant sub-sections of Section 5.

5. STATISTICAL ANALYSIS: DEFINITIONS, DERIVATIONS, CALCULATIONS AND METHODOLOGY

5.1 Subjects Disposition

5.1.1 Disposition and Withdrawals

Disposition and withdrawal data will be collected at Visit 1a and Visit 6/EDV in eCRF and will include the following:

- Date of informed consent/assent;
- Reason for screening failure;
- Date of trial termination;
- Did the subject complete the trial as scheduled (yes, no);
- Reason for the premature trial termination;
- Date of last contact.

Screening failures will be subjects who have been enrolled in the trial (i.e. informed consent form signed/assent form signed), but discontinue the trial before first IMP intake due to the following reasons:

- Inclusion/exclusion criteria
- Withdraw consent
- Lost to follow-up
- Adverse event
- Other

One additional attempt to enroll a subject at screening may be permitted for screening failures if the subject fulfils the eligibility criteria. Both disposition events will be included in the analysis for subjects who were rescreened, i.e., the first disposition event (screening failure with reason) will be included into analysis.

The Trial Termination form must be completed for all subjects that have participated in at least one visit starting from Visit 1b, including subjects dropping out before any IMP intake. The subject information eCRF must be updated to indicate the subject status as Completed or Withdrawn.

Subjects may withdraw or may be withdrawn from the trial for the following reasons:

- at subject's own request (withdrawal of consent/assent)
- if in the investigator's opinion, for reasons of safety or ethics, continuation in the trial would be detrimental to the subject's well-being
- major protocol deviations (rules to consider deviations as minor/major will be documented in the data review report)
- pregnancy
- wish for pregnancy
- development of an exclusion criterion if clinically significant
- adverse event
- at the specific request of the sponsor
- lost to follow-up
- other

In addition to protocol, withdrawn reasons (for subjects who were withdrawn) "At subject's own request (withdrawal of consent)", "If in the investigator's opinion, for reasons of safety or ethics, continuation in the trial would be detrimental to the subject's well-being" and "Other" will be subcategorized as "IMP related", "non-IMP related" and "Uncategorized" by data management. Final decision for subcategorization will be approved by sponsor.

Subjects' disposition table for withdrawals will include further summaries:

- Overall withdrawn reasons;
- Withdrawn reasons by visits;
- Withdrawn reasons by cycles;
- Withdrawn reasons by education level
- Withdrawn reasons by race;
- Withdrawn reasons by ethnicity;
- Withdrawn reasons by BMI groups.

Also, Subjects' disposition table without data from site 140 will be prepared.

Tables

No.	Name	Analysis set	Comments
Table 15.1.1.1.1	Analysis Sets	Enrolled	Number and percentage of subjects included into each analysis set will be presented. Percentage will be based on number of subjects in the ES.
Table 15.1.2.1.1	Screen Failures	Enrolled	Number and percentage of subjects who were enrolled and failed screening will be presented and summarized by reasons associated with the discontinuation. Percentage will be based on number of subjects in the ES.
Table 15.1.3.1.1	Reasons for Exclusion from Analysis Sets	Enrolled	Number and percentage of subjects excluded from SS, FAS and MFAS together with reason(s) for exclusion will be summarized. Percentage will be based on number of subjects in the ES.
Table 15.1.4.1.1	Subjects' Disposition	Safety	The number and percentage of subjects who completed or discontinued study will be summarized. Reasons associated with the termination will be included. Percentage will be based on number of subjects in the SS. Data of centers 104 and 120 will be excluded.
Table 15.1.4.1.2	Subjects' Disposition (Excluding Site 140)	Safety	The number and percentage of subjects who completed or discontinued study will be summarized excluded data from site 140. Reasons associated with the termination will be included. Percentage will be based on number of subjects in the SS. Data of centers 104 and 120 will be excluded.
Table 15.1.5.1.1	Disposition by Attended Visit	Safety	The number and percentage of subjects attended at each visit will be summarized. Percentage will be based on number of subjects in the number of subjects in the SS.
Table 15.1.6.1.1	Disposition by Sites	Safety	The number and percentage of subjects by sites will be summarized. Percentage will be based on number of subjects in the number of subjects in the SS.

Listings

No.	Name	Analysis set	Comments
Listing 16.2.1.1	Reasons for Exclusion from Analysis Sets	Enrolled	Subjects excluded from any analysis set and corresponding reasons for exclusion will be listed.
Listing 16.2.1.2	Subject's Disposition	Safety	Disposition information from trial termination page will be listed.
Listing 16.2.1.3	Subject Visits	Enrolled	Visits' dates will be listed for the subjects from ES.

Figures

No.	Name	Analysis set	Comments
Figure 15.1.1.1	Flow Chart of Subject Disposition	Enrolled	-
Figure 15.1.2.1	Flow Chart of Analysis Sets	Enrolled	-

